4.3.3. Consent and Assent Procedures

Subjects will be asked to verify basic eligibility for the trial prior to enrollment (age, diagnosis, if they currently are on dietary therapy) and to provide a copy of their current medical record at the time of enrollment, if they choose to

participate. Interested subjects will be securely emailed a copy of the consent prior to their enrollment appointment. The Rare Brain Disorders Program maintains a dedicated secure email address ([contact]) for correspondence with current and prospective subjects and research participants. Interested patients may ask any questions via this email, or arrange a phone conversation to answer questions prior to traveling to Dallas for enrollment. [name] or M.D. co-investigator will consent the subjects in a private exam room. Each aspect of the trial will be thoroughly explained to the legal guardian and subject. Time will be allowed for questions to be asked. The physician will explain that participation is voluntary, the decision not to participate does not affect the quality of their standard of care treatment with the physicians, and subjects may withdraw from the study at any time. Subjects age 10 to 17, inclusive, will be asked to sign the assent form, and a legal guardian will be asked to sign the consent form. Subjects under the age of 10 are not required to sign assent. The subject's legal guardian will be asked to sign the consent form for these subjects.

Subjects and legal guardians will also have the HIPAA Authorization for Research explained to them, and again any questions will be answered. The subject's legal guardian will be asked to sign the HIPAA form.

Subjects and their legal guardians will receive a signed copy of both the consent form and the HIPAA Authorization form. One copy will be placed in the research folder, and one copy will be placed in the subject's medical record.

Subjects and their legal guardians will also be able to consent to the study via Redcap or by email.

4.3.4. Group Assignment

This is an open-label study; there is no group assignment.

5. STUDY INTERVENTIONS

5.1. Interventions, Administration, and Duration

5.1.1. Triheptanoin: A triglyceride oil containing three odd-carbon chain-length fatty acids (i.e., a triglyceride of 7-carbon heptanoic acid) manufactured for food applications. Triheptanoin will be taken 4 times per day (approximately every 6 hours: prior to breakfast, lunch and dinner and a mid-afternoon snack) by mouth. It is dosed 4 times per day, divided evenly. Subjects will receive supplementation at the maximum tolerable dose (MTD) determined in Protocol 1 (either 35%, 40%, or 45% of daily caloric intake). Subjects who experience acute gastrointestinal distress (nausea, mild stomach upset, mild diarrhea) may decrease the dose to 50% for two days, then increase the dose over the course of less than a week (in a manner similar to what is described in Protocol 1) until they reach the intended dose. Subjects who are unable to tolerate the maximum tolerable dose will be discontinued from the study. The oil

should be taken approximately one hour before meals, and will be mixed with fat-free, sugar-free yogurt or pudding for administration.

- 5.1.2. Forty-five subjects will be enrolled in a 6 month on/3 month off treatment trial of triheptanoin. Initiation of triheptanoin will be done in the Children's Medical Center Dallas Epilepsy Monitoring Unit.
- 5.1.3. Subjects will not be required to stop other medications. Subjects will be directed to maintain their usual medications, including rescue seizure medications, as necessary for the course of the study. Subjects may have any clinical medical records transferred back to their referring physician at completion of the study.
- 5.1.4. Side Effects: 14 years of experience with C7 diet therapy in children and adults (including our 14 G1D subjects (1), and a larger group of patients with fatty acid oxidation defects) has failed to reveal any dangerous or permanent adverse effects (9, 11, 12, 14). However, subjects may experience mild gastrointestinal upset or stomach pain, and mild diarrhea (1). Both of these side effects are usually resolved by lowering the initial dose of oil by one-half and gradually titrating up to the required dose. In addition, subjects who do not follow the recommendations to reduce other fat intake in their diet may experience weight gain. Careful monitoring of fat and calorie intake has effectively reversed the weight gain. The data indicate no adverse effects on normal metabolism. A side effects questionnaire will be used to track any self-reported side effects. Patient safety information will be updated, if necessary, after completion of this trial.

5.2. Handling of Study Interventions

- 5.2.1. Triheptanoin will be purchased from 1) Stepan Lipid Nutrition headquartered in Maywood, New Jersey, where the company has also a production facility. The oil is supplied in 25 kg containers under a current Material Transfer Agreement (see Letter of Support), and/or 2) CKM Corporation headquartered in Racine, Wisconsin with the production facility in Racine, Wisconsin.
- 5.2.2. Stepan Lipid Nutrition and/or CKM Corporation will distribute the oil to the Investigational Pharmacy Services (IPS) at Children's Medical Center. The pharmacists at the IPS will package the oil for each subject based on oil weight, and provide enough oil for the duration of the study plus a 5% overage to account for spillage and adjustments in dosage. The packaged oil will be given to the research personnel for shipping to the families via FedEx Appointment Home Delivery. This method of delivery provides a confirmed time of delivery and requires an adult signature for delivery. This is a three day shipping time. Subjects will be provided a 4 day supply of C7 oil upon discharge to ensure they have enough to last until the shipment arrives.

5.3. Concomitant Interventions

- 5.3.1. Required Interventions: There are no additional required interventions.
- 5.3.2. Prohibited Interventions: Subjects are prohibited from starting or changing dietary therapy or other oil-based dietary modifications (including ketogenic diet or medium chain triglyceride therapy) while on study protocol. Subjects who feel this change is necessary will be withdrawn from the study for their own protection.
- 5.3.3. Precautionary interventions: [name] or M.D. co-investigator may direct subjects to adjust the dosing of their oil if necessary for tolerability. If subjects experience acute gastrointestinal distress by self-report during treatment initiation, the amount of oil administered will be decreased to 50% of the dose for 2 days, then gradually increased over less than a week until the desired dose is reached. Subjects who are unable to tolerate the maximum tolerable dose of oil will be discontinued from the trial. If subjects experience gastrointestinal distress during the 6 months of treatment (post treatment initiation), the amount of C7 oil will also be decreased as above. Subjects unable to tolerate a return to the required dose will be discontinued from the study. A dietitian will also be available to provide nutritional counseling for subjects who are having difficulties adjusting to the oil, as experience has shown that mixing the C7 oil with an emulsifier, such as yogurt, and other simple dietary interventions can effectively and permanently improve tolerability (based on our previous experience with G1D (1)).
- 5.3.4. Drug treatments during C7 consumption: G1D patients will generally not need to change any concomitant drug treatment as part of this study. Such changes may be initiated by outside local neurologists or by M.D. investigators in this study and prompted by increased seizure frequency or unexpected drug toxicity. While participants will be screened for a stable drug regimen (see Exclusion Criteria) and recognizing that changes in such therapy may occur, the following scenarios will be entertained:
 - 5.3.4.1. No change in type of drug treatment is the planned study conduct. It is likely that this plan will be followed by all subjects because, in clinical practice, the withdrawal of an antiseizure drug on a given patient is usually evaluated only at 2-year intervals, which exceeds the duration of this Protocol. Modest (10-25% dose) changes will be allowed per standard clinical practice in rapidly growing (young) children, whose weight normally increases on a monthly basis. These children will thus continue to be treated per standard pediatric neurological practice.
 - 5.3.4.2. Addition of a new antiseizure drug. This will be prompted by increased seizures and is equivalent to C7 failure.

5.3.4.3. Discontinuation of an antiseizure drug. This will be prompted by drug adverse events and recorded as such (as outlined below). Such events are very unlikely in patients who have been receiving a stable drug regimen (see Exclusion Criteria).

5.4. Adherence Assessment: The coordinator will call subjects and families once a month to determine adherence (by self-report), remind subjects to go in for the month two lab draw if not already done, and assess amount of oil remaining, and will prompt and procure an answer to any questions that the family may have. If any subjects are having trouble as reported during a call, [name] or M.D. co-investigator will be notified and a written plan of action will be developed. Additionally, a nutritional consult will be completed to determine if the C7 dose is still correct. If the subject's caloric intake has changed significantly enough to require a change in the amount of C7 needed, the dietician will consult with PI or M.D. co-investigator, who will contact the family to provide directions for the dose change.

6. CLINICAL AND LABORATORY EVALUATIONS

6.1. Schedule of Evaluations

6.2. Timing of Evaluations

Evaluation	Screen -1 month	Visit 1* Pre-Entry and Entry		Monthly Phone Calls	Visit 2 (± 7 days) 6 mo. on-oil		Visit 3 (± 7 days) 3 mo. off-oil	
		Day 1 Pre-Entry and Entry	Day 2 Entry		Day 1 On oil	Day 2 Off oil	Day 1	Day 2
Informed Consent		X						
Documentation of Disease/Disorder	X	X			X		X	
Medical/Treatment History	X	X			X		X	
Clinical Assessment		X			X		X	
Targeted Physical Exam		X			X		X	
Ataxia Scale		X			X		X	
Clinical Global Impression		X			X		X	
Side Effect Assessment		X		X	X		X	
Pregnancy Testing		X			X			
Neuropsychological tests		X	X		X		X	
Nutritional Assessment		X		X	X		X	
Seizure Count		X		X	X		X	
Inpatient		Admit: Noon	D/C: Noon		Admit: Noon	D/C: Noon	Admit: Noon	D/C: Noon
Continuous EEG		X	X		X	X	X	X
Laboratory Evaluations: Hematology, Chemistry on Day 1 or Day 2		X	X	X	X	X	X	X
Blood collection to measure C7 ketones ¹		X	X		X	X		
Triheptanoin Supplementation			Start			End		

¹Optional

6.2.1. Pre-Entry Evaluations

6.2.1.1. Screening

In order to evaluate subjects' eligibility to participate prior to traveling to Dallas, a waiver of informed consent will be obtained only for the purposes of obtaining information regarding age, diagnosis, height, weight, and current dietary therapy. Once

the subject's basic eligibility has been confirmed, the subject will be scheduled a screening visit in order to be consented and to continue the screening process. We will request that subjects keep a seizure log for one month prior to their screening visit. This information will be collected from the subject on the completion of the consent process. Keeping a month long seizure log does not differ from standard of care. A month long seizure log is normally requested of all subjects whether or not they are participating in a research study.

After signing the informed consent, subjects will finish the screening for study eligibility. All screening evaluations to determine eligibility must be completed within one day prior to study entry. Screening and pre-entry evaluations may occur concurrently. All screening activities are consistent with standard of care. Screening includes documentation of diagnosis, medical history, and pregnancy testing if appropriate.

6.2.1.2. Pre-Entry Day 1

The first day of the subject's visit is Pre-entry Day 1. Pre-entry assessments consist of clinical assessment, targeted physical exam, ataxia rating, clinical global impression, side effect assessment, pregnancy testing if appropriate, and a seizure count. Neuropsychological testing will be conducted in the afternoon of the same day.

6.2.2. On-Study/On-Intervention Evaluations

6.2.2.1. Entry Day 1-2

Subjects will be admitted for a 24 hour inpatient stay for treatment initiation and monitoring. Entry evaluations will be done within a day of pre-entry and consist of a blood draw to evaluate hematology, blood chemistry, and lipid panel. We will also obtain 3 mL of blood that is left over from the samples above (if available) or draw an additional 3 mL of blood to measure C7 ketones. The collection of this blood for measurement of ketones is optional. A continuous EEG will be completed on subjects over the 24 inpatient stay.

Subjects will be started on-intervention on the morning of Day 2 after they fast overnight. We will draw an additional 3 mL of blood to measure C7 ketones. The collection of this blood for measurement of ketones is optional. Subjects will be started on C7 oil at the maximum tolerable dose from Protocol 1, a percentage of age-dependent individual daily caloric intake, divided into 4 doses per day. Subjects will be maintained on continuous EEG for 4-6 hours after the initial C7 administration, then be discharged from their inpatient stay. Subjects will undergo neuropsychological testing on the afternoon of Day 2, ending Visit 1.

6.2.2.2. Months 1-5

Each month between Visit 1 and 2, the research coordinator will contact each family to evaluate adherence and tolerability. Additionally, at month two each subject will complete safety blood work at a local CLIA-certified clinical laboratory and have the

results returned to PI at UT Southwestern Medical Center. Every effort will be made to ensure adherence to the protocol: Subjects who do not comply with the month two blood draw (i.e., those who submit blood work results 10 days or later past the due date) will receive extra guidance via telephone and secure email. The maximum tolerable period for result submission delay is 30 days, after which subjects will be evaluated for termination or, if extenuating circumstances have occurred, may have the delivery of oil delayed until they return to compliance with the protocol. Subjects determined to exhibit greater propensity to delays in the opinion of the research team will receive pre-emptive anticipatory guidance before each blood draw due date and help with local phlebotomy scheduling.

Contingency plans for any pro-epileptogenic effects of C7: This is extremely unlikely since C7 is fully consumed in the TCA cycle as a metabolic fuel source and experience with C7 has failed to show any adverse events, including epilepsy. The EEG in G1D shows preprandial spike-waves in the majority of patients regarding of apparent clinical seizure control, thus providing an individual baseline. To address the potential circumstance that C7 may be associated or coincide with a significant increase in clinical seizure frequency between visits, study exit will be considered. An additional optional procedure will include the performance of a routine outpatient clinical EEG. This procedure will be obtained and reported locally (i.e., in the area of patient residence) in an accredited clinical facility and the report forwarded to the M.D. investigators for the following decisions and interventions after clinical comparison with previous patient EEGs. If the new EEG is deemed significantly more abnormal following clinical neurophysiological evaluation by a board-certified pediatric epileptologist, C7 cessation will be followed by study exit procedures.

6.2.3. Intervention Discontinuation Evaluations

Subjects will return for a discontinuation visit at 6 months after initiation of treatment. Subjects undergo the same set of evaluations completed at enrollment. Subjects will complete a medical history, clinical visit, physical exam, pregnancy test if appropriate, and neuropsychological testing on the first day of the visit. Subjects will undergo a 24 hour inpatient stay with continuous EEG to capture EEG recordings in all states: non-fasting/on oil; fasting/on oil; fasting/off oil; and fasting/on oil. On day 1 or day two, subjects can have blood drawn to evaluate hematology, chemistry, and lipid panel. We will also obtain 3 mL of blood that is left over from the samples above (if available) or draw an additional 3 mL of blood to measure C7 ketones. The collection of this blood for measurement of ketones is optional. Subjects will be administered a final dose of oil on the morning of Day 2 for the purposes of fasting, on oil EEG. At that point, they will be discontinued from the oil and discharged from the inpatient stay.

If subjects wish to discontinue the oil before 6 months, we will ask them to return for a discontinuation visit as soon as feasible and remain on the oil until they return. If subjects wish to discontinue due to intolerable side effects, they will be permitted to do so, and asked to return for a final visit as soon as feasible. Many of our patients come

from out of town, and it could potentially be a matter of weeks to a month before a return visit is possible. Subjects will complete a medical history, clinical visit, physical exam, pregnancy test, and neuropsychological testing on the first day of the exit visit. On day one or day two, subjects will complete a fasting blood drawn to evaluate hematology, chemistry, lipid panel, and specialized metabolites. We will also obtain 3 mL of blood that is left over from the samples above (if available) or draw an additional 3 mL of blood to measure C7 ketones. The collection of this blood for measurement of ketones is optional. Subjects will also have a fasting EEG, and will be discontinued from the study at this visit.

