6.2.4 Final On-Study Evaluations

Subjects will return for a 3 month off-intervention visit, which will essentially repeat the Visit 2 discontinuation visit. Subjects will undergo a medical history, clinical evaluation, physical exam, and neuropsychological testing, then be admitted for 24 inpatient continuous EEG. On day 1 or day 2, subjects will undergo blood work (hematology, chemistry, and lipid panel). This stay will complete their participation, and subjects will be discontinued from the study.

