8. CRITERIA FOR INTERVENTION DISCONTINUATION

Triheptanoin supplementation will be discontinued if any of the following occur:

- Any of the cited or other adverse experiences become intolerable to the subject
- Metabolic syndrome develops as assessed by glucose and lipid profiles
- Any elevation above laboratory normal range in hepatic transaminases or creatinine is noted
- Any clinically relevant blood cell count abnormality develops
- Non-compliance occurs
- Severe intercurrent illnesses take place

Subjects who discontinue due to the above reasons will be asked to return for a final research visit to complete exit procedures and receive referrals for ongoing care if necessary. Subjects who are discontinued due to adverse events will be followed via daily, alternate-day or weekly phone calls to assess resolution of the adverse event.

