9.5. Data Analyses

Summary descriptive statistics: For normally distributed, continuous data, means and standard deviations will be used to describe the demographic and clinical characteristics of the patient population participating in the study and medians and semi-interquartile ranges will be used to describe characteristics of the patient population when the data are continuous, non-normally distributed. For categorical or dichotomous variables, the frequency or the proportion will be reported.

Primary Aim: The primary aim is demonstrating the benefit of C7, as measured by a change in performance on the primary attention measure for each age group. The proportion of subjects who achieved favorable outcome will be estimated along with the corresponding 95% confidence interval using an exact binomial method. We will also investigate if there will be significant differences in the proportions of favorable outcomes among three age groups using Fisher's exact test. We will make every effort to minimize the missing data. We expect minimal amount of missing data. If missing data occurs, missing data will be imputed using multiple imputation techniques.

Generalized estimating equation (GEE) analysis will be used to examine if C7 positively affects other neuropsychological (e.g., IQ, language, processing speed) and neurological performance, such as ataxia over time (baseline, 6 months, and 9 months).

Secondary Aim: A secondary aim is to evaluate the effect of C7 supplementation of a regular diet on an EEG activity and to evaluate the safety of C7 supplementation. EEG will be analyzed in 3 ways (spike-wave duration, total number of seizures and background of the EEG as described above). GEE analysis will be used to examine if there are significant changes in EEG activity and safety over time. GEE analysis will be also conducted to investigate whether attention neuropsychological scores correlate with the EEG findings.

Study end. Statistical analyses at the end of the study will examine the initial measures at baseline, 6 months, and 9 months. Repeated measurement data will be analyzed using the generalized estimating equation (GEE) approach. The GEE method has been widely used for the analysis of repeated measurement data because of its robustness to random missing and misspecification of the true correlation structure.

SAS V9.4 (SAS Institute, Inc. SAS V9.4, Cary, NC, 2014) will be used to analyze the data.

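### Letting safety blood fall on either inpatient day allows glucose, lipids and beta-hydroxybutyrate to be sampled fed at one visit and fasted at another, which adds noise to the single-arm safety contrast and can bias it if the mix shifts

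*Combined protocol and SAP*

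**What the plan says.** The schedule in Section 6.2 has one row for the three inpatient visits: "Laboratory Evaluations: Hematology, Chemistry on Day 1 or Day 2". The text sections follow it:

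- **Visit 1 (6.2.2.1):** "Entry evaluations will be done within a day of pre-entry and consist of a blood draw to evaluate hematology, blood chemistry, and lipid panel". The same section says "Subjects will be started on-intervention on the morning of Day 2 after they fast overnight".
- **Visit 2 (6.2.3):** "On day 1 or day two, subjects can have blood drawn to evaluate hematology, chemistry, and lipid panel". The stay is designed to pass through non-fasting and fasting states, on and off oil, and a final oil dose is given on the morning of Day 2.
- **Early exit (6.2.3):** "On day one or day two, subjects will complete a fasting blood drawn to evaluate hematology, chemistry, lipid panel, and specialized metabolites".
- **Visit 3 (6.2.4):** the draw may again fall on either day. The visit is described as essentially a repeat of Visit 2, and subjects are off oil.
- **Month two (6.2.2.2):** safety blood is drawn at a local laboratory, with no feeding state given.

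Lipid panel, plasma glucose and beta-hydroxybutyric acid are named safety measures in the Synopsis and Sections 1.2 and 9.2.2.3. Section 9.5 says "GEE analysis will be used to examine if there are significant changes in EEG activity and safety over time" and names no term for sample state. Section 8 includes the criterion "Metabolic syndrome develops as assessed by glucose and lipid profiles".

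**The concern.** Glucose, beta-hydroxybutyrate and the feeding-sensitive part of the lipid panel depend on when the subject last ate. (This is general physiology; the documents give no size for it.) The treatment is itself a triglyceride. Section 5.1.1 sets it at 35%, 40% or 45% of daily calories in four equal doses, so each dose carries 35/4 = 8.75% to 45/4 = 11.25% of the day's energy. Section 2.2 accepts that changes in lipids are possible, so these analytes are among those the trial most needs to read cleanly.

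With no control arm, a change between visits cannot be set against a concurrent group sampled under the same rule. If feeding state varies between samples, part of the observed change belongs to the meal and not to C7. No case report form field for time since food or oil is described, so the difference might not be recoverable at analysis. Individual values are affected as well as means: the Section 8 criterion reads glucose and lipid profiles without saying in what state they were taken.

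**Working it through.** **Step 1. Which states does the text permit at each draw?**

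| Draw | Day | Feeding state | Oil |
|---|---|---|---|
| Visit 1 | Day 1 or 2 | Day 1 non-fasting (6.3.9 schedule); Day 2 after overnight fast | Before oil: Section 2.1 places baseline blood ahead of treatment |
| Month two | Local laboratory | Not stated | Time since dose not stated |
| Visit 2 | Day 1 or 2 | Day 1 non-fasting; Day 2 includes fasting states | Day 1 on oil; Day 2 before or after the final dose |
| Visit 3 | Day 1 or 2 | Day 1 non-fasting; Day 2 not stated | Off oil |
| Early exit | Day 1 or 2 | Fasting required | Time since dose not stated |

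Section 9.5 names baseline, 6 months and 9 months as its time points. Within that comparison, feeding state is open at all three visits, but dose timing is open only at Visit 2. Month two lies outside it.

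**Step 2. What could this do to a visit-to-visit change?** The plan has no figure to reproduce here. The following is an illustration with assumed inputs:

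- True C7 effect: zero.
- D: fed-minus-fasted shift, in units of the SD of within-subject change when both samples share a state. Assumed 0.25, 0.5 or 1.
- f, g: share of subjects sampled fed at baseline and at 6 months, taken as independent between visits. Assumed.
- N: 39 (3 × 13 evaluable) to 45 (3 × 15 recruited), from Section 9.3.

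Spurious mean change = (g − f)D. Variance multiplier v = 1 + D²[f(1 − f) + g(1 − g)]. Standard error = √(v/N). The false-positive rate comes from a normal approximation at two-sided 0.05.

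**Equal mix, f = g = 0.5.** The bias is (0.5 − 0.5)D = 0 and v = 1 + 0.5D²:

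| D | v | Confidence interval width × √v | Equivalent N from 39 (39/v) |
|---|---|---|---|
| 0.25 | 1.031 | 1.016 | 37.8 |
| 0.5 | 1.125 | 1.061 | 34.7 |
| 1 | 1.500 | 1.225 | 26.0 |

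The false-positive rate stays at 5.0%. The cost is precision, plus misread changes in individuals whose two samples differ in state.

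**Mix moving in one direction (worst case).** Example with f = 0.25, g = 0.75, D = 0.5, N = 39: bias = 0.5 × 0.5 = 0.25; v = 1 + 0.25 × 0.375 = 1.094; standard error = √(1.094/39) = 0.167; ratio = 1.49; false-positive rate 32%.

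| Fed share, baseline to 6 months | D | Bias (SD) | False-positive rate, N = 39 to 45 |
|---|---|---|---|
| 25% to 75% | 0.25 | 0.125 | 12% to 13% |
| 25% to 75% | 0.5 | 0.25 | 32% to 36% |
| 25% to 75% | 1 | 0.5 | 76% to 82% |
| 0% to 100% | 0.25 | 0.25 | 35% to 39% |
| 0% to 100% | 0.5 | 0.5 | 88% to 92% |
| 0% to 100% | 1 | 1 | about 100% |

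These rates apply only if the mix really moves between visits. Nothing in the documents says that it does.

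**The case against.** The strongest reply is that the same two-day rule covers all three visits and Visit 3 is said to repeat Visit 2, so there is no stated reason for the fed share to drift. If it does not drift, the mean change is unbiased. This stands. A reader might infer from the worst-case rows that the safety analysis is likely to show false C7 effects; the documents do not support that. They permit mixed states, and they neither require them nor indicate a direction.

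Two further inferences also fail. Baseline is not open to contamination by the first dose, because Section 2.1 puts baseline blood before treatment. The month-two sample does not enter the comparison at the Section 9.5 time points.

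It can also be said that safety is defined as no clinically significant change, that laboratory results are compared with normal ranges, and that the GEE supports a secondary aim. The go/no-go thresholds rest on attention, with safety weighed in the intermediate range. All this limits the consequence, but clinical reading of an individual change still depends on knowing the sample state.

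Finally, a fasting outpatient draw would be a real burden. Section 6.2.2.2 reports preprandial spike-waves in most patients, and the Visit 1 fast takes place in hospital on continuous EEG. It is also true that a sample taken only before oil would not show a post-dose lipid rise. Both points shape the fix; neither removes the inconsistency within Section 6.2.3, where the early-exit draw must be fasting and the scheduled draw need not be.

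**Conclusion.** The point holds as a modest, inexpensive improvement. As written, the plan allows glucose, lipids and beta-hydroxybutyrate to be compared across visits in unlike feeding states and, at Visit 2 only, before or after the final oil dose. Early leavers and completers may also be sampled differently.

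The expected harm is noise: about 3% to 50% more variance of change for assumed shifts of 0.25 to 1 SD, with an equal and independent fed/fasted mix. It would be smaller if each subject tended to be drawn in the same state each time. Bias in the mean, and the raised false-positive rates above, require the mix to differ between visits and should be read as a one-way worst case. Neither the shift nor the mix is given in the documents. Blood counts and creatinine are outside the point.

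**What to change.** 1. Reconcile the scheduled and early-exit draws within Section 6.2.3.
2. In Sections 6.2.2.1, 6.2.3 and 6.2.4 and the schedule table, replace the two-day choice for glucose, lipid panel and beta-hydroxybutyrate with one common sample state at the three inpatient visits. Use a state that the stays already contain, for example the Day 2 morning sample after the overnight fast and before any oil that day. Section 6.2.4 does not state a fast, so confirm that Visit 3 includes this state.
3. Record time since last food and last oil dose on the case report form for every safety draw, including month two. No fasting is asked for at the local laboratory.
4. In Section 9.5, either add sample state to the GEE for these analytes or restrict their change analysis to matched-state samples.

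The cost is less scheduling freedom at the inpatient visits and one extra case report form entry. If post-dose lipids are also of interest, the plan should say so and identify those samples separately.
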